7. TRIAL PROCEDURES

7.1 Screening

7.1.1 Informed Consent

The investigator or designee will explain the nature, purpose and risks of the trial to the participant or legally authorized representative (LAR/guardian) and will provide him/her with a copy of the written information and informed consent form (ICF). The participant or LAR will be given sufficient time to consider the trial before deciding whether or not to participate. The participant or LAR will be informed that participation is voluntary and that her/his future medical treatment will not be compromised by participation in the trial and that s/he can withdraw from the trial at any time. The participant or LAR must be willing and able to provide written informed consent before entering the trial. The investigator or a medically qualified designee is responsible for administering and documenting the written informed consent of the participant.

7.1.2 Participant Identification Assignment

After the participant has met eligibility criteria and enrolls into the study, the participant will be assigned a unique 5-digit ID number. This 5-digit number will be used to identify the participant throughout the trial and during the data analysis.

7.2 Visit Procedures

Participants should be instructed to fast, when possible, overnight (at least 8 hours) immediately prior to all at- clinic visits, Screening Visit. While fasting, water is permitted.

7.2.1 Screening Period – Fasting for at least 8 hours, when possible

The screening period will consist of \leq 7 days prior to the randomization visit (Day 0). During the screening period, participants' eligibility criteria must be confirmed. *Patients with clinical suspicion of sepsis will have an initial run-in period of 48 hours while being screened for eligibility for enrollment. Patients with evidence of sepsis at the end of this run-period will be excluded from participation.* Participants or LAR must sign an informed consent prior to initiating any of the screening procedures. Participants who do not fulfill all eligibility criteria cannot continue in the protocol (screening failures).

Screening period procedures are as follows:

- The participant or LAR is to review and sign the informed consent document. Informed consent must be obtained from the participant or LAR before performing any trial related procedures, including screening procedures
- Verify inclusion and exclusion criteria for eligibility
- Assess MELD score.
- Physical exam
- Collect medical history including the alcohol consumption specifics
- Have participants completed the TLFB questionnaire, CLDQ, and AUDIT
- Record vital signs, including height and weight
- Record prior (within 30 days of Day 0) and current concomitant medications
- Perform a baseline standard 12-lead electrocardiogram (ECG), if not already done as standard of care within 7 days of screening
- Assess availability of liver biopsy samples (if applicable) which may have been obtained as part of standard of care
- Obtain blood samples for hematology, hepatic function panel, BMP, and coagulation tests
- Perform a serum pregnancy test in females of childbearing potential
- Perform a PCR test for COVID-19, if not done as SOC.

**The participant should be reminded that fasting (8 hours) is requested, when possible, prior to his/her next visit.

7.2.2 Day 0 Procedures (Randomization) – Fasting for at least 8 hours, when possible

- Collect medical history including the alcohol consumption specifics
- Perform a physical examination
- Record vital signs, including weight
- Assess and record any pretreatment emergent AEs
- Record prior (within 30 days of Day 0) and current concomitant medications, noting any changes from screening, if applicable. Perform a urine pregnancy test in females of childbearing potential, if greater than one day has elapsed since screening pregnancy test.
- Confirm inclusion and exclusion criteria for eligibility
- Assess MELD scores
- Randomize the participant only if s/he meets all inclusion criteria and no exclusion criteria
- Obtain blood samples for hematology, hepatic function panel, BMP, and coagulation tests, **if greater than one day has passed since screening.**
- Obtain biospecimens for specimen banking and measuring anakinra trough levels as outlined in Table 1.
- Dispense study medication and instruct the participant on medication dosing and administration. Instruct the participant to swallow the capsules whole; s/he must not open, chew, divide, open or crush the capsule. Verbally instruct participant and caregiver (if applicable) on subcutaneous injection procedures and provide IRB-approved instruction handout
- The participant should be reminded that fasting (8 hours) is requested, when possible, prior to his/her next visit.

7.2.3 D3 Procedures (\pm 2 days) -- Fasting for at least 8 hours, when possible

- Perform a physical examination
- Record vital signs, including weight
- Assess and record any emergent AEs
- Record any changes to concomitant medications
- Assess MELD scores
- Obtain blood samples for hematology, hepatic function panel, BMP, and coagulation tests
- Obtain biospecimens for specimen banking and measuring anakinra trough levels as outlined in Table 1.
- The participant should be reminded that fasting (8 hours) is requested, when possible, prior to his/her next visit.
- Assess medication compliance form

7.2.4 D7 Procedures (\pm 2 days) – Fasting for at least 8 hours, when possible

- Perform a physical examination
- Record vital signs, including weight
- Assess and record any emergent AEs
- Record any changes to concomitant medications
- Assess MELD and Lille scores.
- Obtain blood samples for hematology, hepatic function panel, BMP, and coagulation tests
- Obtain biospecimens for specimen banking and measuring anakinra trough levels as outlined in Table 1.
- The participant should be reminded that fasting (8 hours) is requested, when possible, prior to his/her next visit.
- Assess medication compliance.
- Calculate Lille score. If >0.45 , participant should stop the bottle Prednisone/placebo.
- Dispense study medication if required by safety lab results (outpatient only.)

7.2.5 Day 14 procedures (\pm 2 days) -- Fasting for at least 8 hours, when possible

- Collect medical history including the alcohol consumption specifics
- Perform a physical examination, including a urine pregnancy test
- Record vital signs, including weight
- Assess and record any emergent AEs
- Record any changes to concomitant medications
- Assess MELD scores
- Obtain blood samples for hematology, hepatic function panel, BMP, and coagulation tests.

- Obtain biospecimens for specimen banking and measuring anakinra trough levels as outlined in Table 1.
- The participant should be reminded that fasting (8 hours) is requested, when possible, prior to his/her next visit.
- Assess medication compliance.

7.2.6 D28, D60 and D 90 Procedures (\pm 7 days) -- Fasting for at least 8 hours, when possible

- Collect medical history including the alcohol consumption specifics
- Perform a physical examination
- Record vital signs, including weight
- The participant is to complete the Alcohol Timeline Follow back
- Assess and record any emergent AEs
- Record any changes to concomitant medications
- Assess MELD scores.
- Obtain blood samples for hematology, hepatic function panel, BMP, and coagulation tests.
- Obtain biospecimens for specimen banking as outlined in Table 1.
- The participant should be reminded that fasting (8 hours) is requested, if possible, prior to his/her next visit.
- Assess medication compliance

7.2.7 Follow up phase D180 (\pm 7 days) – Fasting for at least 8 hours, when possible

- Collect medical history including the alcohol consumption specifics
- Perform a physical examination
- Record vital signs, including weight
- The participant is to complete the Alcohol Timeline Follow back
- Assess and record any emergent AEs
- Record any changes to concomitant medications
- Assess Liver Scores: MELD
- Obtain blood samples for hematology, hepatic function panel, BMP, and coagulation tests.
- Obtain biospecimens for specimen banking as outlined in Table 1.

7.2.8 Missed Visits

Participants who miss a visit will receive a phone call from the coordinator who will read and collect information from the phone script. If a person is unable to be reached by phone, a medical record review will take place.

7.2.9 Early Termination Procedures

Participants who withdraw consent or discontinue treatment prematurely during the Treatment Phase should complete the assessments required on Day 60, if patient is willing. Participants who discontinue prematurely during the Follow-up Phase should complete the assessments required on Day 180.

7.2.10 Unscheduled Safety Visits

The investigator may schedule an at-clinic Unscheduled/Safety Visit at any time if clinically warranted. Unscheduled and/or repeat assessments may be conducted. As appropriate, the designated study physician should be contacted.

7.2.11 Specimen Banking

Specimens to be banked include genomic DNA, blood mononuclear cells, blood (PBMC, serum and plasma), saliva (only until an adequate number of samples are collected determined by PIs), stool (when possible), urine, and liver biopsy when available.

Type specimen collection is site specific.

8. EFFICACY EVALUATIONS Primary Endpoint Survival at 90 days Secondary Endpoints

- Change in Lille score, change in MELD score, development of AKI, multi-organ failure, SIRS, transfer to ICU, changes in liver function will all be evaluated at 7, 30 and 90 days.
- Organ dysfunction: We will measure changes in Sequential Organ Failure Assessment (SOFA) scores and proportions requiring hemodynamic support for MAP < 65 mm Hg and lactate > 2 mmol/l, renal replacement therapy or mechanical ventilation. We will also modify and re-evaluate the SOFA score without platelet counts given that these are usually low in AH.
- Infections and Sepsis: It is now recognized that the endpoints and case definitions related to sepsis may vary depending on what these will be used for (clinical care, research, surveillance, or quality improvement). Given the central role of sepsis as a driver of outcomes, we will not only measure the types of infection but also identify the proportions of those with sepsis, septic shock or quick-SOFA (qSOFA) criteria based on SEPSIS-3 guidance^{2,39}. We will also capture the key parameters needed for various sepsis related endpoint construction aligned by the recent guidance from the European Drug Development Hub (<http://eddh-cro.wixsite.com/fdtsfv>).
- Renal dysfunction: In alignment with guidance from the acute disease quality initiative⁵⁶, we will quantify AKI development and its progression through persistent AKI, acute kidney disease to chronic kidney disease.
- Need for care escalation: Proportion of participants requiring transfer to ICU for care
- Indicators of gut permeability (endotoxin and bacterial 18S DNA) and pro- inflammatory cytokine/chemokines (TNFa, MCP1, IL-6, IL-1 β) will be assessed in serum/plasma samples.
- Survival at day 30 and 180.

Limitations of mortality as an endpoint in AH and plans to overcome these

All-cause mortality is most relevant when mortality is substantial and attributable to a single mechanism in a homogeneous population. Participants with severe AH are highly heterogeneous with respect to disease severity, end organ involvement and the care they receive. Moreover, as in sepsis and heart failure, death involves failure of multiple organs (liver, heart, kidney, lungs) making it hard to ascertain which one is the primary cause of death. This has led to development and regulatory acceptance of composite endpoints including mortality and key parameters driving mortality for acute heart failure trials. We will leverage these guiding principles to construct a novel and innovative key secondary composite endpoint which will include death or worsening of the SOFA score^{4,5} by ≥ 2 points and worsening of modified MELD score by ≥ 2 points. These are associated with mortality and capture the organ recruitment that marks progression of AH towards death. This endpoint will also be validated with respect to reliability, construct-, criterion- and content validity to establish this as a primary endpoint in future trials. We will also model changes in SOFA scores and MELD scores against mortality to further optimize this endpoint and cross-validate it in the observation cohort.

9. SAFETY EVALUATIONS

9.1 Adverse Events

Adverse event (AE) data will be collected from Day 0 through the double-blind phase, until the participant fully completes her/his trial participation at the Follow Up visit.

9.2 Physical Examination and Vital Signs

To assess for clinical findings, the investigator or designee will perform a physical examination at the time points specified in the Schedule of Trial Procedures (Table 1). All above physical exams may be extracted from medical records if patient is inpatient. This includes height only at Screening. The physical examination must include the following:

9.2.1 Physical Examination

- General appearance
- Weight
- Eyes
- Ears, nose, and throat
- Neck
- Respiratory system
- Cardiovascular system
- Abdominal region
- Mental status
- Neurological system

9.2.2 Vital signs

The following vital signs will be assessed at indicated visits: body temperature, sitting heart rate, sitting blood pressure (BP), respiratory rate, body weight in kilograms without shoes, and height in centimeters (screening only). When taking heart rate and BP readings, participants should be seated quietly for a minimum of 3 minutes before the reading is taken.

9.3 Clinical Laboratory

Blood samples for serum chemistry, hematology, and coagulation will be collected at every visit as detailed in the Schedule of Trial Procedures. The number and volume of samples to be collected at each visit will be detailed in a separate document. These tests will be conducted at local laboratories at 8 participating sites.

All participants with laboratory tests containing clinically significant abnormal values should be followed regularly until the values return to normal ranges, until a valid reason for the AE (other than study medication related AE) is identified, or until further follow up is deemed medically unnecessary.

9.4 Other Safety Related Clinical Outcomes

The following clinical outcomes will be assessed:

- Death (from hepatic and non-hepatic related causes)
- Complications of portal hypertension including gastroesophageal bleeding, interventions to manage variceal bleeding (e.g., variceal banding/sclerotherapy or TIPS placement) and diuretic resistant ascites
- Complications of Cirrhosis: new-onset ascites, hepatic encephalopathy, hepatorenal syndrome (type I or II), and spontaneous bacterial peritonitis).
- Hospitalization
- Change to a higher level of care (i.e., floor to ICU) is an SAE

Each of these events including hospitalizations will be adjudicated by the site investigator as expected as part of the natural history of severe AH, or unexpected (e.g., suicide, motor vehicle accident, or myocardial infarction).

10. ADVERSE EVENTS

10.1 Definition of Adverse Events & Reporting Period for Adverse Events

Safety will be assessed in terms of AEs. All AEs, whether observed by the investigator, reported by the participant, noted from laboratory findings, or identified by other means, will be recorded from Day 0 until the participant completes trial participation (D-180).

AEs are defined as any untoward medical occurrence associated with the use of the study medication in humans, whether or not considered related to study medication. An AE (also referred to as an adverse experience) can be any unfavorable and unintended sign (e.g., an abnormal laboratory finding), symptom, or disease temporally associated with any use of the study medication, without any judgment about causality and irrespective of route of administration, formulation, or dose, including an overdose. For this trial, study medication refers to Anakinra, zinc, Prednisone, or placebo in the double-blind phase.

AEs include but are not limited to: (1) a worsening or change in nature, severity, or frequency of condition(s) present at the start of the trial; (2) participant deterioration due to primary illness; (3) intercurrent illness; and (4) drug interaction.

Participants should be questioned in a general way, without leading the participant or asking about the occurrence of any specific symptom. The investigator should attempt to establish a diagnosis of the event based on signs, symptoms, and/or other clinical information. The diagnosis and not the individual signs/symptoms should be documented as the AE. For example, if the underlying disease process is a stroke, it would not be appropriate to record the AE by describing the symptoms “sudden numbness, dizziness, and difficulty speaking.” The AE medical term of “stroke or cerebrovascular accident” should be recorded as it more accurately describes the AE. Following questioning and evaluation, all AEs, whether believed by the investigator to be related or unrelated to the study medication, must be documented in the participant’s medical records, in accordance with the investigator’s normal clinical practice and on the AE source Document. Each AE is to be evaluated for duration, intensity, frequency, seriousness, outcome, other actions taken, and relationship to the study medication.

10.1.1.1 Pretreatment Event(s)

Untoward events that occur during screening phase (prior to randomization) should be recorded as medical history.

10.1.2 Severity of AEs

AEs must be graded for severity (i.e., intensity). A severity category of mild, moderate, or severe, as defined in Table 2, must be entered on the AE source document. It should be noted that the term “severe” used to grade intensity is not synonymous with the term “serious.” For example, severe headache is a severe AE, but may not be a serious AE. The assessment of severity is made regardless of study medication relationship or of the seriousness of the AE.

Table 2: Clinical Description of Adverse Event Severity

Grade	Clinical Description of Severity
1 = Mild	Causing no limitation of usual activities; the participant may experience slight discomfort.
2 = Moderate	Causing some limitation of usual activities; the participant may experience annoying discomfort.
3 = Severe	Causing inability to carry out usual activities; the participant may experience intolerable discomfort or pain.

10.1.3 Relationship of AEs to Study Medication

The investigator will document her/his opinion of the relationship of the AE to treatment with study medication using the criteria outlined in Table 3. An AE for which there is a ‘reasonable possibility’ that the study medication caused the AE is otherwise referred to as suspected adverse reaction (SAR). ‘Reasonable possibility’ means there is evidence to suggest a causal relationship between the study medication and the AE.

Table 3. Relationship of AEs to Study Medication

Relationship	Description
Definite	A reaction that follows a reasonable temporal sequence from administration of the drug or in which the study medication level has been established in body fluids or tissue; that follows a known or expected response pattern to the suspected drug; and that is confirmed by improvement on stopping or reducing the dosage of the study medication, and reappearance of the reaction on repeated exposure.
Probable	A reaction that follows a reasonable temporal sequence from administration of the study medication; that follows a known or expected response pattern to the suspected study medication; that is confirmed by stopping or reducing the dosage of the study medication; and that could not be reasonably explained by other factors.
Possible	A reaction that follows a reasonable temporal sequence from administration of the study medication; that follows a known or expected response pattern to the suspected study medication; but that could readily be produced by a number of other factors.
Unlikely	A reaction that does not follow a reasonable temporal sequence from administration of the study medication; that does not follow a known or suspected response pattern to the suspected study medication; and that could reasonably be explained by known characteristics of the participant’s clinical state.
Not Related	Any event that does not meet the above criteria.

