10.2.3 Reporting SAEs

In agreeing to the provisions of this protocol, the investigator accepts all legal responsibilities for immediate reporting of SAEs to the study designated physician ([name] or his designee) as described below.

Table 4: Requirements for Reporting AEs to Various Stakeholders

	WIRB and Local IRB	NIAAA	DSMB	Other centers	Drug Company	FDA
AEs	Continuing Review	Annual Report	Every 6 months	DSMB reports (every 6 months)	DSMB reports (every 6 months)	Annual Report
TEAEs	Continuing Review	Annual Report	Every 6 months	DSMB reports (every 6 months)	DSMB reports (every 6 months)	Annual Report
SAEs	Continuing Review	2 working days	Every 6 months	DSMB reports (every 6 months)	DSMB reports (every 6 months)	Annual Report
SUSAR	5 days	2 working days	2 working days	2 working days	2 working days	7 days if death 15 days if other
Fatality	If unrelated Follow SAE timeline If related follow SUSAR timeline					

AE: Adverse Event; TEAS: Treatment Emergent Adverse Event; SAE: Serious Adverse Event; SUSAR: Serious Unsuspected Adverse Reaction; DSMB: Data and Safety Monitoring Board

The study designated physician for AlcHepNet - 02 is [name], who as the IND holder will assume the responsibility of monitoring safety concerns internally and serve as the liaison between the AlcHepNet and the DSMB.

All SAEs must be reported to the DCC-IU (i.e., within 2 working days) after the investigator identifies the SAE. SAEs should be entered into the REDCap system within 2 working days of the investigator becoming aware of the event. An initial report by telephone should then be followed, as soon as possible, by completion of the SAE CRF. Any supporting source documentation should be emailed to the assigned contact information as soon as possible. At a minimum the following information should be provided at the time of the initial report: 5-digit Study ID, a description of the event, at least one criterion classifying the event as Serious and the name and title of the reporting individual. Additionally, judgment of causality by the investigator must be provided as soon as possible to ensure timely reporting to regulatory authorities.

Following the initial report, any additional information obtained by the investigator about the SAE must be reported promptly to the DCC-IU.

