The site investigator will assess whether the event is causally related to the study medication. The study designated physician ([name]) will consider the investigator's assessment, however, since [name] holds the IND and is primarily responsible for the overall safety of the participants, his causality assessment will take precedence over that of the site investigator. The study designated physician will determine if an SAE meets the criteria for an IND safety report (suspected, unexpected serious adverse reaction (SUSAR) in accordance with the FDA regulations, 312.32(c)(1)(i).

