11.3.1 AEs

AEs will be labeled according to standard medical terminology using the case report forms provided. Summary tables of treatment-emergent AEs will be provided. A TEAE is any AE that newly appeared, increased in frequency, or worsened in severity following initiation of study medication. The incidence of TEAEs will be tabulated by system organ class and preferred term for each treatment group, and by severity and relationship to treatment. Tables of TEAEs leading to study medication discontinuation and SAEs will be provided.

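### Read literally, Table 3 grades well-timed reactions with no recognised pattern, and some recognised ones without dechallenge, as Not Related, against the reasonable-possibility definition beside it

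*Combined protocol and SAP*

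**What the plan says.** Section 10.1.3 has the site investigator record an opinion on the "relationship of the AE to treatment with study medication using the criteria outlined in Table 3". That table is the only graded causality scale in the documents. Its five grades work as follows.

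- **Definite** needs plausible timing (or a measured drug level) for a reaction "that follows a known or expected response pattern to the suspected drug; and that is confirmed by improvement on stopping or reducing the dosage", plus recurrence on re-exposure.
- **Probable** needs plausible timing, the same recognised pattern, and an event "that is confirmed by stopping or reducing the dosage of the study medication; and that could not be reasonably explained by other factors".
- **Possible** needs plausible timing and an event which "follows a known or expected response pattern to the suspected study medication; but that could readily be produced by a number of other factors", with or without dechallenge.
- **Unlikely** needs all three of: implausible timing, no known or suspected pattern, and an explanation in the participant's clinical state.
- **Not Related** is "Any event that does not meet the above criteria".

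The paragraph above the table defines a suspected adverse reaction by reasonable possibility, that is, by evidence pointing to a causal link. It does not say which grades meet that test.

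The grade or relatedness is used elsewhere. Section 11.3.1 tabulates TEAEs by system organ class and preferred term, "and by severity and relationship to treatment". The fatality row of Table 4 (Section 10.2.3) reads "If unrelated Follow SAE timeline If related follow SUSAR timeline". Section 10.3 extends follow-up after the final visit to AEs graded possibly, probably or definitely related. Section 6.6.2.1 lets the care team request unblinding for other SAEs thought probably related.

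**The concern.** A causality scale should rise as the evidence rises. This one does not. All three related grades require that the reaction is already recognised, so a new toxicity cannot reach any of them, however strong the evidence in the individual case. Implausible timing is a condition of Unlikely, so a well-timed new toxicity cannot land there either and drops to the residual class.

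The second gap concerns recognised reactions. Definite and Probable need improvement on stopping or reducing the drug, which a fatal reaction cannot show. Possible needs competing causes. A recognised reaction with neither falls through to Not Related.

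At stake are the relationship tables, which would undercount related events, and the other rules that use the grade. Acute kidney injury illustrates this. Section 10.2.3 names it as an adverse event of interest, yet the risk tables in Section 2.3 list it for none of the three drugs. If known or expected is read against those tables (an assumption, since the Investigator's Brochure may list more), a well-timed case could not be graded even Possible.

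**Working it through.** The plan states no figure here to reproduce. The check is to write the five rows of Table 3 as logical rules and run every coherent case through them.

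**Inputs, all from Table 3:** timing (T), recognised pattern (K), improvement on dechallenge (D), recurrence on rechallenge (R, only possible after D), alternative cause (A).

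**Rules** (the drug-level alternative to T matters only for Definite):

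- Definite: T and K and D and R
- Probable: T and K and D and not A
- Possible: T and K and A
- Unlikely: not T and not K and A
- Not Related: everything else

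**Well-timed cases.** K has 2 states, the dechallenge/rechallenge history has 3, and A has 2: 2 × 3 × 2 = 12 profiles.

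| Pattern | Dechallenge / rechallenge | No other cause | Other cause |
|---|---|---|---|
| Recognised | none | **Not Related** | Possible |
| Recognised | dechallenge only | Probable | Possible |
| Recognised | both positive | Definite | Definite |
| Not recognised | none | **Not Related** | **Not Related** |
| Not recognised | dechallenge only | **Not Related** | **Not Related** |
| Not recognised | both positive | **Not Related** | **Not Related** |

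Totals: 2 Definite, 1 Probable, 2 Possible, 7 Not Related. The 7 are 6 of 6 without a recognised pattern and 1 of 6 with one.

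**Two inversions.**

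1. In the first row, removing the alternative cause lowers the grade from Possible to Not Related. Fatal anaphylaxis shortly after an anakinra injection, a listed risk in Section 2.3, is such a case: improvement on stopping cannot be seen and no other cause is present.
2. A badly timed event with no pattern and a disease explanation is Unlikely. A well-timed new event with positive rechallenge is graded below it.

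**Finer grid.** Add drug level (2 states) and split A into none, reasonable but not several, and many; let timing vary: 2 × 2 × 2 × 3 × 3 = 72 profiles. Assume that any alternative explanation satisfies the clinical-state condition of Unlikely.

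- No recognised pattern, well timed: 18 of 18 Not Related.
- No recognised pattern, badly timed: 12 of 18 Unlikely, 6 of 18 Not Related.
- Recognised, well timed, no dechallenge: Not Related with no other cause (2 of 2), Possible with many (2 of 2).
- Recognised, well timed, with a reasonable alternative but not several: also Not Related unless rechallenge is positive.

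**Against the neighbouring definition.** Positive dechallenge and rechallenge are evidence of a causal link, so such a reaction is a suspected adverse reaction under the text of Section 10.1.3 and Not Related under its table. The two cannot both stand.

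**The case against.** The strongest reply is that the site grade does not decide expedited reporting. Section 10.2.3 sends every SAE, whatever its grade, to the DCC-IU within 2 working days. The study designated physician then determines whether it is a "suspected, unexpected serious adverse reaction (SUSAR) in accordance with the FDA regulations", and that physician's causality assessment overrides the site's. The regulation and the reasonable-possibility test give that role a standard independent of the table. This stands, and it rules out several readings that a reader might infer:

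- **That the table closes or contradicts the SUSAR pathway.** It does not, for the reasons just given.
- **That every unexpected reaction is graded Not Related.** This holds only with plausible timing; 12 of the 36 no-pattern profiles in the finer grid are Unlikely. Nor do the documents equate unexpected, in the SUSAR sense, with lacking a recognised pattern.
- **That all such events would be misgraded in practice.** The counts are logical profiles, not event frequencies, and sites record an opinion.
- **That DSMB notice of a death slips from 2 working days to 6 months.** Table 4 has those entries, but Section 10.2.3 also promises the DSMB unblinded SAE data monthly, so that delay is not shown.

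Other limits also stand. Follow-up under Section 10.3 also covers events of other clinical significance. Section 6.6.2.1 has unblinding grounds that need no causality grade, and the relationship tables are descriptive.

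What the reply leaves untouched is the grade itself. The override sits in the SAE reporting text; nothing says that non-serious AEs are regraded before the Section 11.3.1 tables are made. For a fatal case, the FDA entries of Table 4 still differ between an annual report and 7 days according to relatedness, unless the physician changes the site's grade.

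**Conclusion.** The defect is real and should be corrected. Applied as written, Table 3 puts 7 of 12 well-timed profiles in Not Related: all 6 without a recognised pattern, whatever the dechallenge and rechallenge result, and the recognised one with neither dechallenge nor another cause. This is inconsistent with the definition of a suspected adverse reaction in the same section. Site grades would be too low wherever they feed the TEAE relationship tables, the related/unrelated split for deaths in Table 4, the grade-based part of post-trial follow-up and the probably-related ground for unblinding.

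The conclusion assumes that sites apply the rows literally. It says nothing about how many events would be affected, and it touches no efficacy analysis, error rate, power or sample size.

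**What to change.** Reword Table 3 and the text above it.

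1. **Possible:** remove the recognised-pattern requirement. Let it cover plausible timing with some evidence of a causal role, whether or not the pattern is already known and whether or not other factors could explain the event.
2. **Probable:** require confirmation by stopping or reducing the dosage only where this can be assessed.
3. **Not Related:** stop using it as the residual class. Define it as clearly due to another cause and keep it distinct from Unlikely. Check that every profile then has exactly one grade; Unlikely will need widening to take the cases that currently default to Not Related without a clear other cause.
4. **Mapping:** state that Possible, Probable and Definite correspond to reasonable possibility, meaning evidence that suggests causation. A looser bar, that a causal role merely cannot be excluded, would fall below the protocol's own definition. Reconcile this with the SUSAR and fatality rows of Table 4.

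Of the 7 profiles now graded Not Related, the 4 unrecognised ones with positive dechallenge would become at least Possible. So would the recognised one with no other cause, which becomes Probable where dechallenge cannot be assessed. That is 4 + 1 = 5; the remaining 2 (unrecognised, no dechallenge) would turn on the evidence in the case.

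The cost is an amendment to one table and its matching form guidance. Somewhat more events will be graded Possible and need SUSAR review.
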